## 412 **2.2.2 Study Eye Criteria**

413  
414 The subject must have one eye meeting all of the inclusion criteria and none of the exclusion  
415 criteria listed below.  
416

417 A subject can have only one study eye. If both eyes are eligible at the time of enrollment, the  
418 study eye will be selected by the investigator and subject before enrollment.  
419

### 420 Inclusion

421 To be eligible, the following inclusion criteria for the study eye must be met:

- 422 1. Presence of cataract for which cataract surgery is scheduled.
- 423 2. Presence of microaneurysms or at least mild non-proliferative diabetic retinopathy (level 20  
424 or higher) on clinical exam.
- 425 3. Visual acuity light perception or better.
- 426 4. Zeiss Stratus OCT central subfield thickness <250 microns (or spectral domain OCT  
427 equivalent)

### 428 429 Exclusions

430 The following exclusions apply to the study eye only:

- 431 1. An ocular condition, other than cataract and diabetic macular edema, is present such that, in  
432 the opinion of the investigator, visual acuity might be affected now (e.g., foveal atrophy,  
433 pigment abnormalities, dense subfoveal hard exudates, nonretinal condition, epiretinal  
434 membrane or vitreo-macular traction) or during the course of the study (e.g., vein occlusion,  
435 uveitis or other ocular inflammatory disease, neovascular glaucoma, etc.).
- 436 2. History of major ocular surgery (including vitrectomy, scleral buckle, any intraocular  
437 surgery, etc.) within prior 4 months or major ocular surgery other than cataract anticipated  
438 within the next 4 months following enrollment.

## 439 440 **2.3 Screening Evaluation and Baseline Testing**

### 441 **2.3.1 Historical Information**

442 A history will be elicited from the subject and extracted from available medical records. Data to  
443 be collected will include: age, gender, ethnicity and race, diabetes history and current  
444 management, other medical conditions, as well as ocular diseases, surgeries, and treatment.  
445

446 **2.3.2 Baseline Testing Procedures**

447 The following procedures are needed to assess eligibility and/or to serve as baseline measures for  
448 the study.

- 449       • If a procedure has been performed (using the study technique and by study certified  
450 personnel) as part of usual care, it does not need to be repeated specifically for the  
451 study if it was performed within the defined time windows specified below.
- 452       • The testing procedures are detailed in the DRCR.net Procedures Manuals (Visual  
453 Acuity-Refractive Testing Procedures Manual, OCT Testing Procedures Manual,  
454 Digital Fluorescein Angiography Procedures Manual, Study Procedures Manual, and  
455 photography procedure manuals). Visual acuity testing, ocular exam, and OCT will  
456 be performed by DRCR.net certified personnel.
- 457       • Maximum time windows from the completion of each procedure to the day of surgery  
458 have been established.
- 459

460 1. Electronic-ETDRS visual acuity testing at 3 meters using the Electronic Visual Acuity  
461 Tester (including protocol refraction) in each eye. (*within 28 days prior to surgery*)

- 462       • *This testing procedure has been validated against 4-meter ETDRS chart testing.*
- 463       • *If the E-ETDRS visual acuity letter score is 0, then counting fingers, hand motion,*  
464 *and light perception are assessed.*

465 2. OCT on the study eye (*within 28 days prior to surgery*)

- 466       • OCTs may only be graded by the reading center if determined likely to need manual  
467 grading

468 3. Ocular examination on the study eye including slit lamp and dilated fundus examination.  
469 (*within 28 days prior to surgery*)

470 4. Laboratory Testing- HbA1c

- 471       • *HbA1c does not need to be repeated if available in the prior 3 months. If not*  
472 *available at the time of enrollment, the subject may be enrolled but the test must be*  
473 *obtained within 3 weeks after enrollment.*

474

475 **2.4 Enrollment of Eligible Subjects**

476 Prior to enrollment, the following should be confirmed:

477 1. The subject's understanding of the study and commitment to the follow-up schedule.

478 2. The subject is scheduled for cataract surgery, and the surgery date is within 28 days after the  
479 baseline assessments.

480

## CHAPTER 3. CATARACT SURGERY

481  
482  
483  
484  
485  
486  
487  
488  
489  
490  
491  
492  
493  
494  
495  
496  
497  
498  
499  
500  
501

### **3.1 Introduction**

The cataract surgery itself is not part of the experimental design. As such, cataract surgeons will not be considered investigators for this protocol and surgical centers will not be involved with the research.

### **3.2 Surgical Procedure**

The cataract surgery, including pre-operative and post-operative assessments and management, should be by the usual manner of each cataract surgeon. The surgical notes and post-op records (specifically the operative report including medications used and any surgical complication, as well as post-operative exams) will be obtained by the clinical site through a record release requested by the subject.

### **3.3 Rescheduling or Cancellation of Surgery**

If surgery is not completed on the scheduled date, the surgery should be rescheduled as soon as possible. If surgery is rescheduled more than 28 days after baseline assessments were completed, the baseline measurements should be reassessed prior to the new surgery date. If the subject is no longer eligible for the study on reassessment, he/she may be dropped.

502  
503  
504  
505  
506  
507  
508  
509  
510  
511  
512  
513  
514  
515  
516  
517  
518  
519  
520  
521  
522  
523  
524  
525  
526  
527  
528  
529  
530  
531  
532  
533  
534  
535  
536  
537  
538  
539  
540  
541  
542  
543  
544  
545  
546

## CHAPTER 4. FOLLOW-UP VISITS AND TREATMENT

### 4.1 Visit Schedule

The schedule of protocol-specified follow-up visits is as follows:

- 4±1 weeks and 16±2 weeks following cataract surgery.
- Additional visits to occur as needed based on usual care.

All treatment is at the discretion of the cataract surgeon and the investigator. Information will be collected on the treatments received pre-operatively, peri-operatively, and post-operatively for DME or CME (topical drops, laser, corticosteroids, anti-VEGF drugs, oral medications, vitrectomy, or others).

The first time any treatment for DME or CME other than topical drops is to be given, an additional visit will be completed at which OCT and fluorescein angiography will be performed prior to administering treatment.

### 4.2 Testing Procedures

The following procedures will be performed at each protocol visit unless otherwise specified. All of the testing procedures do not need to be performed on the same day, provided that they are completed within the time window of a visit and prior to initiating any treatment.

Testing procedures at unscheduled visits are at investigator discretion. However, procedures that are performed should follow the standard DRCRnet protocol for each procedure.

1. E- ETDRS visual acuity testing in each eye (best corrected).
  - A protocol refraction in the study eye is required at all protocol visits. Refraction in the nonstudy eye is not required. When a refraction is not performed, i.e. at unscheduled visits, the most-recently performed refraction is used for the testing.
  - If the E-ETDRS visual acuity letter score is 0, then counting fingers, hand motion, and light perception are assessed.
2. OCT on the study eye
  - OCTs may only be graded by the reading center if determined likely to need manual grading
3. Ocular exam on study eye including slit lamp examination and dilated fundus examination.
4. Fluorescein angiography
  - Obtained at 16 week visit for all study eyes if OCT CSF  $\geq 250$  microns and treatment for DME (other than topical treatments) has not been given. If FA is to be obtained based on this criterion, the eye will be classified by the investigator as one of the following:
    - (1) **CME Only:** Presence of post-surgical CME as defined below, without the presence of DME.  
Post-surgical CME is defined as the presence of ALL of the following:
      - a. CSF  $\geq 250$  microns on OCT

562 **CHAPTER 5.**  
563 **MISCELLANEOUS CONSIDERATIONS IN FOLLOW-UP**

564  
565 **5.1 Complications of Cataract Surgery**

566 Complications of cataract surgery are managed by the cataract surgeon as judged indicated.  
567

568 **5.2 Treatment of Macular Edema in Nonstudy Eye**

569 Treatment of DME in the nonstudy eye is at investigator discretion.  
570

571 **5.3 Diabetes Management**

572 Diabetes management is left to the subject's medical care provider.  
573

574 **5.4 Subject Withdrawal and Losses to Follow-up**

575 A subject has the right to withdraw from the study at any time. If a subject is considering  
576 withdrawal from the study, the principal investigator should personally speak to the subject about  
577 the reasons, and every effort should be made to accommodate the subject.  
578

579 The goal for the study is to have as few losses to follow-up as possible. The Coordinating Center  
580 will assist in the tracking of subjects who cannot be contacted by the site. The Coordinating  
581 Center will be responsible for classifying a subject as lost to follow-up.  
582

583 Subjects who withdraw will be asked to have a final closeout visit at which the testing described  
584 for the protocol visits will be performed.

585 Subjects who withdraw or are determined to have been ineligible post-enrollment may be  
586 replaced in the enrollment total.  
587

588 **5.5 Discontinuation of Study**

589 The study may be discontinued by the Executive Committee prior to the preplanned completion  
590 of follow-up for all subjects.  
591

592 **5.6 Contact Information Provided to the Coordinating Center**

593 The Coordinating Center will be provided with contact information for each subject. Permission  
594 to obtain such information will be included in the Informed Consent Form. The contact  
595 information may be maintained in a secure database and will be maintained separately from the  
596 study data.  
597

598 Phone contact from the Coordinating Center will be made with each subject in the first month  
599 after enrollment and may be made prior to the follow-up visits. Additional phone contacts from  
600 the Coordinating Center will be made if necessary to facilitate the scheduling of the subject for  
601 follow-up visits. A subject-oriented newsletter and a study logo item may be sent.  
602

603 Subjects will be provided with a summary of the study results in a newsletter format after  
604 completion of the study by all subjects.  
605

606 **5.7 Subject Reimbursement**

607 The study will be paying the subject \$25 per completed protocol visit to cover travel and other  
608 visit-related expenses. Payment will be made from the Coordinating Center. Additional travel  
609 expenses may be paid or reimbursed via gas cards for subjects with higher expenses.

610

611 **5.8 Medical Records**

612 Subjects will sign a record release to obtain operative and postoperative records from the cataract  
613 surgeon's office.

614  
615  
616  
617

## CHAPTER 6. ADVERSE EVENTS

618

### **6.1 Events to be Reported**

619 Surgical complications and other untoward events will be recorded on the follow-up exam forms  
620 and not on separate adverse event forms since the cataract surgery is not considered part of the  
621 experimental design.

622

### **6.2 Reporting Requirements for Adverse Events**

624 Each Principal Investigator is responsible for abiding by reporting requirements specific to  
625 his/her IRB.

626

### **6.3 Risks**

627

#### **6.3.1 Risks of Cataract Surgery**

628  
629 Cataract surgery is part of the routine eye care of all subjects in this trial. In some cases  
630 retrobulbar or peribulbar injection may be used to anesthetize the eye and to reduce eye  
631 movements during cataract surgery. Complications of retrobulbar injections are rare. They  
632 include, but are not limited to, the following: retrobulbar hemorrhage (bleeding behind your  
633 eyeball); perforation of the eye by the needle; damage to the optic nerve; diplopia lasting up to  
634 24 hours or more; ptosis lasting up to 24 hours or more; difficulty speaking or breathing;  
635 lightheadedness/syncope/vasovagal response; allergy to any components of the injection; life  
636 threatening response due to the spread of anesthesia to the brain stem, resulting in seizures,  
637 drowsiness, confusion, loss of ability to talk, convulsions, stoppage of breathing, or stoppage of  
638 heartbeat. All of these complications are rare.

639  
640 Complications of the cataract surgery itself include the development of post-surgical cystoid  
641 macular edema 1% to 2% of the time in people with or without diabetes, transient or sustained  
642 increase in intraocular pressure which could lead to glaucoma or blindness, corneal edema from  
643 endothelial cell loss, iris abnormalities, loss of vitreous, retinal tear or detachment, posterior  
644 vitreous detachment, epiretinal membrane, ptosis, diplopia, decentration of IOL, opacity of  
645 capsule, retained cataract remnants.

646

#### **6.3.2 Risks of Eye Examination and Tests**

648 The procedures in this study are part of daily ophthalmologic practice in the United States and  
649 pose no additional known risks. Dilating eye drops will be used as part of each exam.  
650 There is a rare risk of an allergic response to the topical medications used to anesthetize the eye  
651 or dilate the pupil. Dilating drops rarely could cause an acute angle closure glaucoma attack, but  
652 this is highly unlikely since the subjects in the study will have had their pupils dilated many  
653 times previously.

654

#### **6.3.3 Fluorescein Angiography**

656 In the fluorescein angiogram procedure, a yellow dye is injected intravenously. Risks include  
657 but are not limited to: transient change in skin and urine color; nausea; allergic reaction to the  
658 dye; anaphylaxis and possible death (less than 1 in 100,000 people). The procedure will not be  
659 performed if medically contraindicated.

660

#### **6.3.4 Optical Coherence Tomography**

662 OCT carries no known risk. Dilating eye drops will be used as part of each exam.  
663  
664

665  
666  
667  
668

## CHAPTER 7. STATISTICAL METHODS

669  
670  
671  
672

### 7.1 Overview

669 The approach to sample size and statistical analyses are summarized below. A detailed statistical  
670 analysis plan will be written and finalized prior to the completion of the study. The analysis plan  
671 synopsis in this chapter contains the framework of the anticipated final analysis plan.

672  
673 The primary objective of the study is to determine the incidence of progression to center-  
674 involved diabetic macular edema (DME) 16 weeks after cataract surgery in eyes with diabetic  
675 retinopathy and without definite center-involved DME. The incidence rates will be determined  
676 separately for each of the following subgroups:

- 677  
678 1. Eyes in which no injection for DME was received recently prior to surgery or at the  
679 time of surgery\*, each to be further stratified by whether or not there was a history of  
680 any other prior treatment for DME:
- 681 a) No center involved DME and no non-center involved DME (i.e. no DME)
    - 682 • *(CSF <190 for women or CSF <210 for men, and all ISF <260, and all*
    - 683 *OSF <220)*
  - 684 b) No center involved DME and definite/uncertain non-center involved DME
    - 685 • *(CSF <190 for women or CSF <210 for men, and at least 1 ISF ≥260*
    - 686 *or OSF ≥220)*
  - 687 c) Uncertain center involved DME and no non-center involved DME
    - 688 • *(CSF 190 to 249 for women or CSF 210 to 249 for men, and all ISF*
    - 689 *<260, and all OSF <220)*
  - 690 d) Uncertain center involved DME and definite/uncertain non-center involved  
691 DME
    - 692 • *(CSF 190 to 249 for women or CSF 210 to 249 for men, and at least 1*
    - 693 *ISF ≥260 or OSF ≥220)*
- 694 2. Eyes with an injection for DME received recently prior to surgery or at the time of  
695 surgery\*, stratified by whether the treatment was corticosteroids or anti-VEGF  
696 therapy.

697  
698 \* Intravitreal or peribulbar corticosteroids within the last 4 months prior to surgery or  
699 on the day of surgery; anti-VEGF therapy within the last 2 months prior to surgery or  
700 on the day of surgery.

701  
702

### 7.2 Sample Size

703 Recruitment is planned for a period of up to 24 months. Distribution of enrolled eyes in the  
704 predefined subgroups as listed in section 7.1 will be evaluated after 6 months and a  
705 determination will be made at that time whether to continue or stop enrollment.

706  
707 A maximum of 100 eyes in the subgroup with no center involved DME and no non-center  
708 involved DME (group 1a; with/without prior treatment for DME) will be enrolled. Once this  
709 goal is met, recruitment may be stopped in this subgroup. Overall, a maximum of 500 subjects  
710 will be enrolled with no restriction on the number per site.

713 If the rate of progression is 5% in each of these groups (and if N=50 with prior treatment group  
 714 and N=50 without prior treatment group), the half width of the confidence intervals would be  
 715 around 6% with this sample size.  
 716

Proportion progressed to edema	Half-width of 2-sided 95% CI		
	N=50	N=75	N=100
0.05	0.06	0.05	0.04
0.10	0.08	0.07	0.06

717  
 718 **7.3 Statistical Analysis Plan**

719 **7.3.1 Primary Outcome**

720 **7.3.1.1 Primary Analysis**

721 As stated in section 7.1, the primary objective of the study is to determine the incidence of  
 722 progression to center-involved diabetic macular edema (DME) 16 weeks after cataract surgery in  
 723 eyes with diabetic retinopathy and without definite center-involved DME. The incidence rates  
 724 at the 16 week time point will be determined separately for each of the predefined subgroups as  
 725 listed in section 7.1. Progression to edema will be defined separately according to the predefined  
 726 subgroup, as detailed below. Point estimates and 95% confidence intervals will be evaluated for  
 727 each. Similar analyses will be conducted at the 4-week visit.  
 728

729 Within each of the subgroups of eyes with no center involved DME and no non-center involved  
 730 DME (group 1a; one subgroup with prior treatment for DME and one subgroup without prior  
 731 treatment for DME), the following will be evaluated:

- 732 a. Proportion of eyes that progressed to definite center involved edema, defined as  
 733 meeting any of the following criteria:  
 734 (1) OCT central subfield thickness  $\geq 250$  microns at 16 weeks and increased at  
 735 least 1 log OCT unit from baseline to 16 weeks  
 736 (2) Increased at least 2 log units from baseline to 16 weeks  
 737 (3) Any treatment for DME or CME other than topical drops was received after  
 738 surgery, and criterion (1) or (2) was met prior to starting treatment
- 739 b. Of the eyes that did not progress to definite center involved edema above, proportion  
 740 of eyes that progressed to definite non-center involved edema, defined as meeting any  
 741 of the following criteria:  
 742 (1) At least 1 ISF  $\geq 310$  microns at 16 weeks and the maximum corresponding ISF  
 743 increased at least 1 log unit from baseline to 16 weeks OR at least 1 OSF  
 744  $\geq 290$  microns at 16 weeks and the maximum corresponding ISF increased at  
 745 least 1 log unit from baseline to 16 weeks  
 746 (2) At least 1 ISF increased at least 2 log units from baseline to 16 weeks OR at  
 747 least 1 OSF increased at least 2 log units from baseline to 16 weeks  
 748 (3) Any treatment for DME or CME other than topical drops was received after  
 749 surgery, and criterion (1) or (2) was met prior to starting treatment
- 750 c. Proportion of eyes that progressed to at least definite non-center involved edema (i.e.,  
 751 met either definition above).

752 Within each of the other subgroups of eyes, the following will be evaluated:

- 753 a. Proportion of eyes that progressed to definite center involved edema, defined as  
 754 meeting any of the following criteria:  
 755 (1) OCT central subfield thickness  $\geq 250$  microns at 16 weeks and increased at  
 756 least 1 log unit from baseline to 16 weeks

- 757 (2) Increased at least 2 log units from baseline to 16 weeks  
758 (3) Any treatment for DME or CME other than topical drops was received after  
759 surgery, and criterion (1) or (2) was met prior to starting treatment  
760

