## 218 **1.2 Study Objectives**

219 The objective of the study is to determine the incidence of progression to center-involved  
220 macular edema 16 weeks after cataract surgery in eyes with diabetic retinopathy and without  
221 definite center-involved DME. The incidence rates will be determined separately for each of the  
222 following subgroups:

223

224 1. Eyes in which no injection for DME was received recently prior to surgery or at the time  
225 of surgery\*, each to be further stratified by whether or not there was a history of any  
226 other prior treatment for DME:

227

a) No center involved DME and no non-center involved DME (i.e. no DME)

228

- *(central subfield [CSF]<190 for women or CSF<210 for men, and all inner subfields [ISF]<260, and all outer subfields [OSF]<220)*

229

b) No center involved DME and definite/uncertain non-center involved DME

231

- *(CSF <190 for women or CSF<210 for men, and at least 1 ISF  $\geq$ 260 or OSF $\geq$ 220)*

232

c) Uncertain center involved DME and no non-center involved DME

233

- *(CSF 190 to 249 for women or CSF 210 to 249 for men, and all ISF <260, and all OSF<220)*

234

d) Uncertain center involved DME and definite/uncertain non-center involved DME

237

- *(CSF 190 to 249 for women or CSF 210 to 249 for men, and at least 1 ISF  $\geq$ 260 or OSF $\geq$ 220)*

238

239 2. Eyes with an injection for DME received recently prior to surgery or at the time of  
240 surgery\*, stratified by whether the treatment was corticosteroids or anti-VEGF therapy.

241

242 \* Intravitreal or peribulbar corticosteroids within the last 4 months prior to surgery or on the day  
243 of surgery; anti-VEGF therapy within the last 2 months prior to surgery or on the day of surgery.

244

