##### 291 Primary outcome:

292 Within each of the subgroups of eyes with no center involved DME and no non-center involved  
293 DME (group 1a; with/without prior treatment for DME), the following will be evaluated:

- 294 a. Proportion of eyes that progressed to definite center involved edema, defined as  
295 meeting any of the following criteria:
- 296 (1) OCT central subfield thickness  $\geq 250$  microns at 16 weeks and increased at  
297 least 1 log unit from baseline to 16 weeks
  - 298 (2) Increased at least 2 log units from baseline to 16 weeks
  - 299 (3) Any treatment for DME or CME other than topical drops was received after  
300 surgery, and criterion (1) or (2) was met prior to starting treatment
- 301 b. Of the eyes that did not progress to definite center involved edema above, proportion  
302 of eyes that progressed to definite non-center involved edema, defined as meeting any  
303 of the following criteria:
- 304 (1) At least 1 ISF  $\geq 310$  microns at 16 weeks and the maximum corresponding ISF  
305 increased at least 1 log unit from baseline to 16 weeks OR at least 1 OSF  
306  $\geq 290$  microns at 16 weeks and the maximum corresponding ISF increased at  
307 least 1 log unit from baseline to 16 weeks

- 308 (2) At least 1 ISF increased at least 2 log OCT units from baseline to 16 weeks  
 309 OR at least 1 OSF increased at least 2 log units from baseline to 16 weeks  
 310 (3) Any treatment for DME or CME other than topical drops was received after  
 311 surgery, and criterion (1) or (2) was met prior to starting treatment  
 312 c. Proportion of eyes that progressed to at least definite non-center involved edema (i.e.,  
 313 met either definition above).

314 Within each of the other subgroups of eyes, the following will be evaluated:

- 315 a. Proportion of eyes that progressed to definite center involved edema, defined as  
 316 meeting any of the following criteria:  
 317 (1) OCT central subfield thickness  $\geq 250$  microns at 16 weeks and increased at  
 318 least 1 log unit from baseline to 16 weeks  
 319 (2) Increased at least 2 log units from baseline to 16 weeks  
 320 (3) Any treatment for DME or CME other than topical drops was received after  
 321 surgery, and criterion (1) or (2) was met prior to starting treatment  
 322

323 Secondary analyses on primary outcome: Evaluate potential baseline factors associated with the  

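### The outer-subfield arm of criterion b(1) tests the rise in the inner subfield, so some outer-only thickening of one to under two log units goes uncounted in group 1a components b and c

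*Protocol*

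**What the plan says.** The primary outcome for group 1a has three components: (a) progression to definite center involved edema, (b) progression to definite non-center involved edema among eyes not meeting a, and (c) either of the two. They are defined in the same way in the synopsis (1.3 G) and in 7.3.1.1.

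Component b can be met in three ways:

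- **b(1), ISF arm:** an ISF of at least 310 microns at 16 weeks, with a rise of at least one log unit in the corresponding ISF.
- **b(1), OSF arm:** this is joined as an alternative ("increased at least 1 log unit from baseline to 16 weeks OR at least 1 OSF"), with a threshold of 290 microns on the OSF. The change condition then reads "microns at 16 weeks and the maximum corresponding ISF increased at" least one log unit, so the change is again taken from the ISF.
- **b(2):** a rise of at least two log units in an ISF, or, with no ISF condition, "least 1 OSF increased at least 2 log units from baseline to 16 weeks".
- **b(3):** non-topical treatment was given after "surgery, and criterion (1) or (2) was met prior to starting treatment".

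Group 1a eyes start with every ISF below 260 microns "and all outer subfields [OSF]<220" microns (1.2 and 7.1). The protocol does not say how large a log unit is.

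**The concern.** The progression rules follow one pattern: a thickness threshold plus a one-unit rise, or a two-unit rise alone, with both tests on the same subfield. Component a does this for the central subfield. The ISF arm of b(1) and the ISF part of b(2) do it for the inner ring. Only the OSF arm of b(1) crosses from one ring to the other. The protocol gives no reason for this and does not say which ISF corresponds to a given OSF. The likeliest explanation is that ISF was carried over where OSF was meant, though that is an inference.

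Components b and c are listed under the primary outcome for both group 1a strata. Component b is where thickening outside the center has to be detected. Because b(3) refers back to b(1), the same condition applies to eyes treated before 16 weeks. Section 7.3.1.1 also plans similar analyses at 4 weeks, so the wording would carry over to them. An analyst who follows the text would misclassify some eyes.

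**Working it through.** **The plan's own figure.** Section 7.2 gives half-widths of the two-sided 95% interval. The Wald formula 1.96 × √(p(1−p)/n) gives:

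| p | n=50 | n=75 | n=100 |
|---|---|---|---|
| 0.05 | 0.0604 | 0.0493 | 0.0427 |
| 0.10 | 0.0832 | 0.0679 | 0.0588 |

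All six agree with the printed table after rounding. None depends on the ISF/OSF wording.

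**Which eyes the rule treats differently.** Let s be the size of one log unit in log10. One unit multiplies thickness by 10^s and two units by 10^(2s). Consider an eye that does not meet component a, whose OSF reaches 290 microns or more, and whose ISF rises by less than one unit.

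- It fails both arms of b(1) as written, because both need an ISF rise of one unit.
- It meets b(2) only if its OSF reaches baseline × 10^(2s).
- If the OSF's own rise were tested, it would meet b(1) once its OSF reached both 290 and baseline × 10^s.

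The eyes lost are therefore those with a 16-week OSF from max(290, baseline × 10^s) up to, but not including, baseline × 10^(2s).

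**Smallest OSF rise possible in group 1a.** Baseline OSF is below 220, so reaching 290 means a ratio above 290/220 = 1.318, or more than 0.120 log10.

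**At an assumed s = 0.1.** One unit is ×1.259 and two units ×1.585. Every group 1a eye reaching 290 has already risen by more than one unit. Since 290/1.585 = 183.0, an eye with a baseline OSF of about 183 or lower meets b(2) on reaching 290, and nothing is lost. The gap runs over baselines of about 184 to 219.

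Example: OSF 200 to 300 with ISF 240 to 255.

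- OSF rise: 300/200 = 1.5, or 0.176 log10. This is more than one unit and less than two; b(2) would need 200 × 1.585 = 317.
- ISF rise: 255/240 = 1.0625, or 0.026 log10. This is less than one unit.
- The eye is not counted as written, but would be counted if the OSF's own rise were tested.

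**Range over the undefined step** (16-week OSF values lost, in microns, given no one-unit ISF rise):

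| s (log10) | baseline 180 | baseline 200 | baseline 219 |
|---|---|---|---|
| 0.05 | none | none | none |
| 0.10 | none | 290 to <317 | 290 to <347 |
| 0.15 | 290 to <359 | 290 to <399 | 309 to <437 |
| 0.20 | 290 to <452 | 317 to <502 | 347 to <550 |

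**Direction of the error.**

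- If 2s is at most 0.120 (s about 0.06 or less), every group 1a eye reaching 290 already meets b(2), so no eye is lost.
- If s lies between about 0.06 and 0.12, a one-unit OSF rise is automatic on reaching 290. The rule as written can then only lose eyes.
- If s exceeds about 0.12, the rule can also add eyes. At s = 0.15, take OSF 215 to 295 (295/215 = 1.372, or 0.137 log10, under one unit) with ISF 200 to 290 (1.45, or 0.161 log10, over one unit). This eye counts as written. It would not meet an OSF-to-OSF rule, the 310-micron ISF arm, or b(2).

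**Scale.** Section 7.2 plans on the premise "If the rate of progression is 5% in each of these groups" with 50 eyes per stratum, which is 0.05 × 50 = 2.5 expected events. If that rate applied to component c, one misclassified eye would move the estimate by 1/50 = 2 percentage points, against a half-width of about 6.

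**The case against.** The strongest objection concerns scope. A reader might infer that edema confined to the outer subfields is missed altogether. The text does not support that, because b(2) counts any OSF rise of two log units or more whatever the ISF does. A reader might also infer that the error can only lose events. That holds only if a log unit is no larger than about 0.12 log10, and at about 0.06 or less nothing is lost. Both the existence and the direction of the bias therefore rest on a step size the protocol does not give. Nor is the stated primary objective affected: it is progression to center-involved edema, which is component a and uses only the central subfield.

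It can also be said that the detailed analysis plan, which is not at hand, might correct the wording, and that the document has no data on how often outer-only thickening occurs. Both are fair, and they rule out any claim about how many eyes would be lost.

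The wording itself remains a defect. It reads the same in both places, and nothing elsewhere in the protocol corrects it. Section 7.1 calls this chapter the framework for the later plan, so a plan that tested the OSF's own rise would have to depart from the protocol on a primary-outcome definition.

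**Conclusion.** The point holds in a limited form. The OSF arm of b(1) measures change on the wrong ring, out of line with every other progression rule in the protocol. Followed as written, it leaves out of group 1a components b and c, including through b(3), eyes whose OSF reaches 290 microns with an OSF rise of one to under two log units and no one-unit ISF rise.

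Its extent depends on the undefined log unit. At an assumed 0.1 log10 it is confined to baseline OSF of about 184 to 219 microns with a 16-week OSF below 1.585 times baseline. It vanishes at about 0.06 or less. Above about 0.12 it is accompanied by possible false additions. The share of eyes affected cannot be worked out from the document. Component a, groups 1b to 1d, group 2 and the precision table stand as they are.

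**What to change.** In both 1.3 G and 7.3.1.1, reword the second arm of b(1) so that it requires an OSF of 290 microns or more at 16 weeks together with a rise of at least one log unit, from baseline to 16 weeks, in the corresponding OSF. State the size of a log unit once, where the progression criteria are first given, so that the one-unit and two-unit rules can be applied without assumption.

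The cost is a change of subfield in two places and one added definition. It needs no new measurements, since b(2) already requires OSF thickness at baseline and 16 weeks, and no sample-size figure changes. It should be settled before the outcome is programmed.
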